**Figure 1 Study Design**

- a. Doses shown in this figure may be modified based on emerging data. Four to six cohorts *will be evaluated in the SAD part of the study with a dose range between 40 mg and 170 mg.*
- b. *Two to three cohorts will be evaluated in the MAD part of the study. Doses in the MAD part will not exceed the dose considered to be safe and well-tolerated in the SAD part.*

### **3.1.2 Dose Escalation Decision Criteria**

A Safety Review Meeting will be conducted by the Principal Investigator and the Sponsor Clinical Team prior to each dose escalation.

The decision to escalate to the next dose level in the SAD cohorts will be based primarily on the available safety and tolerability information through Day 4 (including adverse events [AEs], electrocardiograms [ECGs], vital signs, clinical laboratory test results) and, secondarily, on available PK and PD data through 24 hours post-dose at the previous dosage level. In addition, all available safety and PK data from the previous dose level(s) will be reviewed. The anticipated dose escalation sequence for the SAD is 40 mg, 100 mg, 140 mg and 170 mg (See [Table 1](#)).

The decision to escalate to the next dose level in the MAD cohorts will be based primarily on the safety and tolerability information (including AEs, ECGs, vital signs, clinical laboratory test results) through Day 14 and secondarily on available PK data. In addition, all available safety and PK data from the previous dose level(s), including SAD cohorts, will be reviewed.

Depending on the evaluation of the safety and/or PK data: the same dose may be repeated; a lower dose may be administered; or intermediate dose escalation steps other than those anticipated above may be used at the discretion of the Study Investigator and the Sponsor.

The recommendation for the subsequent cohort dose level will be shared with the Ethics Committee.

### **3.1.3 Treatment Stopping Rules**

Any serious adverse event (SAE) considered related to study drug will lead to an immediate halt of study drug dosing and enrollment of new subjects until a thorough investigation has been conducted by the Sponsor's Clinical Team and the Principal Investigator. The sponsor or designee will notify all investigators and IRBs/EC regarding the outcome of such investigation, and the study will only continue if agreed by the IRBs/EC.

Planned dose escalation will be stopped if one of the following circumstances occurs in subjects dosed with RO7020531, unless it is apparent that the occurrence is not related to the administration of study medication:

- Within a cohort, three or more subjects on active drug experience:
- Severe and clinically significant (as defined by the Investigator) RO7020531-related AEs of the same character, or
- Clinically significant RO7020531-related laboratory abnormalities of the same character, or
- Clinically significant RO7020531-related changes in vital signs or ECGs of the same character (e.g., confirmation of mean corrected QT interval [QTc] 500 msec or 60 msec longer than the pre-dose baseline).
- Within two consecutive dose cohorts, four occurrences of any of the above conditions in subjects receiving active drug.
- Any other findings (regardless of the incidence rates) that, at the joint discretion of the Sponsor and the Investigator, indicate dose escalation should be halted.
- Dose escalation will not proceed if it is predicted that higher doses of RO7020531 will not result in a further increase in RO7011785 plasma exposure; or if the mean systemic exposure (AUC) reaches the RO7011785 plasma levels found to be associated with dose-limiting toxicities in the global EIH study.

If dose escalation is stopped, lower doses could be investigated by mutual agreement between the Sponsor and the Investigator.

For an individual subject in the MAD cohorts, dose continuation will not occur if the subject experiences any of the following:

- Clinically significant RO7020531-related changes in safety parameters that are considered not acceptable by the Investigator and/or the Sponsor; or
- Poor tolerability, which is considered to affect the subject's well-being and/or the PK evaluation.

Due to the exploratory nature of this clinical study, its conduct can be discontinued at any time at the discretion of the Sponsor.

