### **3.1.1.2      Multiple Ascending Dose Study**

The trigger to start the first cohort in the MAD includes documentation of adequate safety and tolerability in the SAD cohorts and evidence of PD effects. For a given dose evaluated in the SAD, evidence in at least two subjects exhibiting responses above placebo-defined baseline for select PD biomarkers, including *the protein and metabolite markers IFN- $\alpha$ , IP-10, TNF- $\alpha$ , IL-6, IL-10, IL-12p40 and neopterin and markers of transcriptional responses (ISG15, OAS-1, MX1 and TLR7)*, should be demonstrated. If the next dose in the SAD has been considered safe, then the previous dose demonstrating TLR-associated PD activity will be considered as the starting dose for the MAD. In addition, the starting dose/exposure in the MAD part of this study should have been considered safe in the global EIH study (NP39305). Only doses covered by the dose range evaluated in the SAD part will be used in the MAD, and two to three dose levels will be evaluated (Figure 1).

[figure not shown]
Once criteria have been reached to determine an initial dose for MAD, subjects will be screened up to 28 days before enrollment into the MAD part of this study. They will be asked to remain in the unit from Day -2 until Day 14 with QOD dosing initiated on Day 1. In total, 7 QOD doses will be administered with the last dose given on Day 13. Subjects will be discharged on Day 14. After completing 7 QOD doses, each subject in the MAD cohorts will return for an outpatient follow-up visit 7 days after the last dose. All subjects will have a follow-up phone call 28 days after their last dose. Subjects will be asked to report any AEs that occur during this period.

Upon safety review of the MAD cohort(s) data, dose escalation will proceed in the MAD part of this study. The maximum dose investigated in MAD will not exceed doses

evaluated in the SAD part of this study nor will it exceed doses and exposures considered to be safe and with acceptable tolerability in the global EIH study.

Based on the PK, PD and safety evaluation of the previous dose cohorts, additional cohorts of subjects may be enrolled at higher or lower dose levels, or at a dose level already tested.

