#### **4.3 METHOD OF TREATMENT ASSIGNMENT AND BLINDING**

This study is observer-blinded. This means that the subjects, the Investigator, and all individuals in direct contact with the subjects at the investigative site will be blinded, except for the pharmacy staff handling the study drug distribution.

This study is Sponsor-open; members of the Sponsor's project and study teams who do not have direct contact with the subjects will be unblinded. This may exclude contract research organization (CRO) staff in direct contact with the site.

Healthy volunteers will be randomized 4:1 to RO7020531 or to placebo in each dose cohort. The randomization numbers will be generated by the Sponsor or its designee. The randomized treatment assignment will be allocated from the list sequentially to subjects in the order in which they are randomized. A minimum of two females per cohort will be randomized, with at least one female receiving active drug. The treatment allocation will be managed by the unblinded site pharmacist(s) and will be based on the randomization code list.

To allow informed recommendations or decisions regarding the dose decisions in this study, an integrated assessment of the available data on PK, select PD, safety and tolerability will be made prior to each dose decision.

In exceptional cases, (e.g., if deemed important for dose decisions or for the more thorough evaluation of safety-related concerns that may impact dosing of future subjects on this or other currently conducted or shortly to start studies involving administration of RO7020531) and in the interest of the subjects' safety, the Investigator may be unblinded after approval by the Clinical Pharmacologist.

The Principal Investigator(s) will receive a set of sealed treatment codes. These may have the form of sealed envelopes or scratch codes. If the identity of the test medication needs to be known in order to manage the healthy volunteer's condition, the treatment code for that healthy volunteer may be broken.

As per Health Authority reporting requirements, the Sponsor will break the treatment code for all unexpected serious adverse events (see Section 5.1) that are considered by the Investigator to be related to study drug.

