### **5.1.2        Serious Adverse Events (Immediately Reportable to the Sponsor)**

A serious adverse event is any adverse event that meets any of the following criteria:

- Fatal (i.e., the adverse event actually causes or leads to death).
- Life-threatening (i.e., the adverse event, in the view of the Investigator, places the subject at immediate risk of death).

This does not include any adverse event that had it occurred in a more severe form or was allowed to continue might have caused death.

- Requires or prolongs inpatient hospitalization (see Section 5.3.5.9).
- Results in persistent or significant disability/incapacity (i.e., the adverse event results in substantial disruption of the healthy volunteer's ability to conduct normal life functions).
- Congenital anomaly/birth defect in a neonate/infant born to a mother exposed to study drug.
- Significant medical event in the Investigator's judgment (e.g., may jeopardize the healthy volunteer or may require medical/surgical intervention to prevent one of the outcomes listed above).

The terms “severe” and “serious” are not synonymous. Severity refers to the intensity of an adverse event (rated as mild, moderate, or severe, or according to a pre-defined grading criteria (see Section 5.3.3); the event itself may be of relatively minor medical significance (such as severe headache without any further findings).

Severity and seriousness need to be independently assessed for each adverse event recorded on the eCRF.

Serious adverse events are required to be reported by the Investigator to the Sponsor immediately (i.e., no more than 24 hours after learning of the event; see Section [5.4](#) for reporting instructions).

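### A cluster of severe, related but non-serious reactions in a running MAD cohort stops dose escalation, but no rule pauses repeat dosing for the cohort's other subjects

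*Combined protocol and SAP*

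**What the plan says.** Section 3.1.3 of the protocol has three levels of stopping rule.

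- **Related serious event.** It "will lead to an immediate halt of study drug dosing and enrollment of new subjects", and the study resumes only with ethics committee agreement.
- **Count rule.** "Planned dose escalation will be stopped if one of the following circumstances occurs in subjects dosed with RO7020531". The within-cohort form needs three or more active subjects with "Severe and clinically significant (as defined by the Investigator) RO7020531-related AEs of the same character", or with clinically significant related laboratory, vital-sign or ECG changes of the same character.
- **Individual rule.** "For an individual subject in the MAD cohorts, dose continuation will not occur if the subject experiences any of the following": an unacceptable related safety change, or poor tolerability.

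Stopping anyone else is discretionary: the Investigator under 5.2.1, the Investigator or Sponsor under 4.7.1, and the Sponsor for the whole study under 3.1.3 and 4.7.2. Section 3.1.2 adds that "The decision to escalate to the next dose level in the MAD cohorts will be based primarily on the safety and tolerability information", with data taken through Day 14. The last MAD dose is on Day 13.

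On information flow, section 4.3 blinds the Investigator, while members of the Sponsor's project and "study teams who do not have direct contact with the subjects will be unblinded". Section 5.4 sets a 24-hour limit for serious events, non-serious events of special interest and pregnancies. Section 5.1.3 confines special interest to a combined liver finding and suspected transmission of an infectious agent. Other adverse events go on the eCRF and to the Sponsor with no stated time (5.3).

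**The concern.** The plan already treats three similarly affected active subjects as enough to bar a higher dose. It states no default for repeat doses, in the same cohort, of the dose that produced those reactions. In the SAD part this matters less, because each subject receives one dose. In the MAD part each subject has seven, 48 hours apart, and stopping escalation does nothing for a cohort that is still being dosed.

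Events that are severe but not serious are foreseeable. Table 2 grades as severe an event that prevents work or normal daily activity, and 5.1.2 keeps severity and seriousness apart, with severe headache as its example. Section 5.2.1 expects dose-dependent flu-like symptoms, headache among them, within hours of dosing. At stake is the protection of healthy volunteers who, by 1.3.2, have no direct benefit.

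**Working it through.** **1. The plan's own figure.** Section 6.1 gives a 90% chance of at least one event among eight active subjects at a true incidence of 25%. 1 − (1 − 0.25)^8 = 0.8999, so it reproduces. Eight active subjects per cohort is the base used below.

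**2. The rules side by side, for a cluster in a running MAD cohort.**

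| Situation | Affected subjects | Escalation | Other subjects in the cohort |
|---|---|---|---|
| At least one event judged serious and related | Dosing halted | Halted | Dosing halted |
| Three or more active, severe and related, none serious | Individual rule | Stopped | No stated rule; discretion only |

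I looked for contrary text in 3.1.2, 4.3, 4.5.1, 4.6.1.4, 4.7, 5.1 to 5.4 and 7.2. None requires a pause for the unaffected subjects.

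**3. Doses exposed to the gap.** Doses fall on Days 1, 3, 5, 7, 9, 11 and 13, so a cohort has 8 × 7 = 56 active doses. Assume that all subjects are dosed on the same days, exactly three active subjects are affected and stopped, no event is judged serious, and nobody uses discretion. After dose k, the other five active subjects still have 5 × (7 − k) doses scheduled.

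| Cluster after dose | Doses remaining | Share of 56 |
|---|---|---|
| 1 | 30 | 54% |
| 2 | 25 | 45% |
| 4 | 15 | 27% |
| 6 | 5 | 9% |

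**4. How often the threshold would be met.** The documents give no severe-event rate for multiple doses, so the rates here are assumptions. For X ~ Binomial(8, p), P(X ≥ 3) is 0.6% at p = 5%, 3.8% at 10% and 32% at 25%.

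Section 1.2.2 reports 80 NP39305 volunteers in eight single-dose cohorts, with every adverse event mild. Assuming eight active per cohort, no severe event in 64 active subjects gives a one-sided 95% upper bound of 1 − 0.05^(1/64) = 4.6%; at that rate P(X ≥ 3) is 0.5%. Restricting to 100, 140 and 170 mg (24 active), the bound is 1 − 0.05^(1/24) = 11.7%, and P(X ≥ 3) is 5.7%. These are single-dose data and do not bound the multiple-dose rate, but they make 25% an extreme scenario for severe events.

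**5. Could the serious-event halt close the gap?** If each of three events had an independent chance q of being judged serious, the halt would fire with probability 1 − (1 − q)^3: 27%, 58% and 88% at q = 10%, 25% and 50%. The values of q are assumed, and independence is doubtful for events of the same character. The range shows only that the halt may or may not apply; nothing below relies on it.

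**The case against.** The strongest reply is that the powers to stop exist and are close to the subjects. MAD subjects live in the unit from Day −2 to Day 14 with adverse events collected daily. The Investigator sees each event, judges severity and relatedness, and can discontinue anyone without treatment codes. An event that "may jeopardize the healthy volunteer or may require medical/surgical intervention to prevent one of the outcomes listed above" can be classed as serious, which brings in the full halt. The MAD dose may not exceed doses evaluated in the SAD part, "nor will it exceed doses and exposures considered to be safe and with acceptable tolerability in the global EIH study". The Sponsor also has ways to hear early: 4.5.1 requires consultation before an adverse event is treated, 4.6.1.4 requires notification of QTc outliers, and 7.2 asks for timely eCRF data.

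Most of this stands, and it rules out several readings that a reader might infer:

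- *That nobody can stop the cohort, or that blinding prevents the Investigator from acting.* Not supported. Codes are needed for the formal active-drug count, not to withhold a dose.
- *That safety goes unreviewed until Day 14.* Not supported. Day 14 is the data cut for the escalation decision; Appendix 4 schedules laboratory tests on Days 4, 8, 11 and 13.
- *That the Sponsor has no early route to the information.* Not supported, given the three routes above.
- *That about half the doses would be given after a cluster.* Not supported. That is an upper bound under inaction by both parties.

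What the reply does not supply is a default. Discretion leaves open what happens to the cohort at the plan's own threshold. The dose caps make a cluster less likely but do not say what follows one. The consultation rule exempts paracetamol and urgent need, so flu-like symptoms might bypass it; the QTc rule covers ECG findings only. None of the three routes sets a time limit for severe related non-serious events.

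**Conclusion.** The point holds as a cheap safety improvement, not as a fatal defect. At the within-cohort threshold in 3.1.3, with no event judged serious, the only stated consequence is that escalation stops. Pausing the unaffected subjects rests on judgement, and the party that can make the formal count has no stated time by which it must learn of severe related events.

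The exposure is at most 30 of 56 active doses, and only if the cluster follows dose 1, three active subjects are affected and nobody uses discretion. A trigger is probably uncommon, given the mild single-dose experience, but the multiple-dose rate is unknown from these documents. The conclusion rests on the wording of the rules, not on any assumed event rate.

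**What to change.** Two additions, with the thresholds unchanged.

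1. **Section 3.1.3.** When the existing within-cohort count is met in a MAD cohort, further dosing of that cohort and enrolment into it pause until the Sponsor and Investigator have jointly reviewed the events.
2. **Section 5.4.** In the MAD part, a severe adverse event judged related to study drug is reported to the Sponsor within 24 hours, so that the unblinded Sponsor can do the active-drug count. For reactions noticed within hours of dosing, that fits inside the 48-hour dosing interval.

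Keep the single-subject QTc notification in 4.6.1.4 as it is. A separate reporting duty for laboratory, vital-sign and other ECG changes is not needed; it would add a second trigger, and its deadline would be unclear where blood is drawn before the dose, as on Days 11 and 13.

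**Cost.** At assumed severe related rates of 5% to 25% in all ten subjects, the extra reports number 10 × 0.05 = 0.5 to 10 × 0.25 = 2.5 per cohort, or 1 (two cohorts at 5%) to 7.5 (three at 25%) over the MAD part. If a pause fires, the every-other-day schedule breaks and that cohort may lose its Day 13 PK and PD profile. At assumed true rates of 5% or 10%, the severe-event count would trigger a pause in 0.6% or 3.8% of cohorts.

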### **3.1.4 Length of Study**

**SAD:** The total duration of the study will be up to 9 weeks (from Screening through study completion) for each randomized subject as follows:

- Screening: Up to 28 days;
- Dosing period: 1 day;
- Follow up: 28 days after dosing.

The in-clinic period will be from Day –2 until Day 3.

**MAD:** The total duration of the study will be up to 10 weeks (from Screening through study completion) for each randomized subject as follows:

- Screening: Up to 28 days;
- Dosing period: 14 days;
- Follow-up: 28 days after last dosing.

### **3.1.5 End of Study**

The end of the study is defined as the date when the last subject last observation (LSLO) occurs. LSLO is expected to occur 6 weeks after the last subject is randomized.

## **3.2 RATIONALE FOR STUDY DESIGN**

### **3.2.1 Rationale for Dosage Selection and Dosage Regimen**

The dose selection for this study is supported by the non-clinical safety data and may be modified based on the clinical data collected from the global EIH study, NP39305. The current study in Chinese healthy volunteers (YP39553) is planned to consist of four to six dose levels in SAD and two to three dose levels in MAD, which will be within the dose-range considered to be safe and with acceptable tolerability in the global EIH study, NP39305.

Based on the non-clinical data with RO7020531 (see Section 1.2.1), the half-life of the active TLR7 agonist RO7011785 is relatively short. However, previous experience in monkeys and humans with another TLR7 agonist (RO6864018) indicate that a short exposure of the TLR7 agonist initiates a series of pharmacodynamic events with biomarker activity that peaks as late as 48 hours post dose. Similar results are

anticipated following dosing with RO7020531 and are supported by activity measured in non-clinical models.

*In the ongoing global EIH study (NP39305), all dose levels tested in SAD (3 mg – 170 mg) have been observed to be safe and well tolerated. In SAD Cohort 6 (100 mg), 3/8 healthy volunteers demonstrated increases in interferon alpha and which met the predefined criteria for TLR7 marker activity.*

The starting dose of 40 mg was selected for the SAD portion of this study in Chinese patients based on the safety and tolerability documented in the study NP39305, avoiding very low doses/exposures that may not produce pharmacodynamic effects, while ensuring appropriate safety margins expected with the first dose.

The phenomena of response priming (increase in PD effects with the second dose) and tachyphylaxis (reduced response with chronic and frequent doses) are expected with RO7020531 based on clinical and non-clinical data observed with another TLR7 agonist, RO6864018. The phenomenon of TLR7 priming was frequently observed with RO6864018 in cynomolgus monkeys after the second dose administration and was followed by a subsequent response tachyphylaxis. Similarly, in healthy volunteers and HCV patients (Study ANA773-601), there is evidence of response priming with QOD schedule of RO6864018 showing an increase in PD response with the second dose, and evidence of tachyphylaxis to systemic IFN with repeated dosing on QOD schedule.

The QOD schedule has been selected for the multiple dosing part of this study based on information acquired from non-clinical studies with RO7020531 and clinical studies with RO6864018, and is aimed to optimize PD responses while minimizing safety risks, such as poor tolerability with every day dosing.

Based on clinical data with another TLR7 agonist (Study ANA773-601), it is expected that priming of PD effects and tachyphylaxis to systemic IFN release provided by the QOD schedule might be a desirable effect that can potentially limit AEs, and improve tolerability and efficacy.

### **3.2.2 Rationale for Study Population**

Healthy subjects were chosen for this SAD and MAD study to allow (in a safe and well-controlled setting) better understanding of the tolerability, safety and PK of oral dosing with RO7020531 while avoiding the confounding variables of co-medications and co-morbidities found in HBV patients. Another prodrug, RO6864018, which is rapidly converted to the TLR7 agonist, RO6871765, has been tested in both healthy volunteers, hepatitis C virus (HCV) and is being tested in an ongoing study in HBV patients. Data from single and multiple dose administrations indicate that PK/PD relationships determined in healthy volunteers and HCV patients were comparable. These in house data and other literature data with TLR7 agonists comparing healthy volunteers and CHB patients indicate that PD/dose relationships determined in healthy volunteers, CHB

and HCV patients were comparable, suggesting that healthy volunteers represent a suitable population for the evaluation of safety, tolerability, PK and PD of TLR agonists that will be predictive of the dose-effect relationships anticipated in CHB patients.

Healthy status in study subjects will be confirmed during the screening period. Due to immunomodulatory mechanism of action of RO7020531, all subjects with a history of immunologically mediated disease will be excluded. All healthy volunteers will be tested for autoimmune markers to exclude participants with potential connective tissue disease or other immune-mediated diseases.

In this SAD and MAD study, each cohort will include ten subjects (eight active, two placebo). Sex differences in TLR7-mediated response have been reported, including higher immune activation and IFN- $\alpha$  production by pDCs in females ([Berghofer et al 2006](#)). Females appear to be more sensitive to TLR7 activation than males and exhibit greater PD responses in peripheral blood such as fold change from baseline for several genes and cyto/chemokines investigated in previous clinical studies of another TLR7 agonist, RO6864018. It was also shown that female healthy volunteers appeared to have higher exposure of the active TLR7 agonist, RO6871765. These facts warrant further investigation in this study, and so, to allow evaluation of potential sex differences in PK and PD response, a minimum number of two female subjects per cohort (with at least one female receiving active drug) is implemented in each one of the study cohorts.

